8.4 UNANTICIPATED PROBLEMS

8.4.1 DEFINITION OF UNANTICIPATED PROBLEMS

This protocol uses the definition of Unanticipated Problems as defined by the Office for Human Research Protections (OHRP). OHRP considers unanticipated problems involving risks to participants or others to include, in general, any incident, experience, or outcome that meets all of the following criteria:

- Unexpected in terms of nature, severity, or frequency given (a) the research procedures that are described in the protocol-related documents, such as the Institutional Review Board (IRB)-approved research protocol and informed consent document; and (b) the characteristics of the participant population being studied;
- Related or possibly related to participation in the research ("possibly related" means there is a reasonable possibility that the incident, experience, or outcome may have been caused by the procedures involved in the research); and
- Suggests that the research places participants or others at a greater risk of harm (including physical, psychological, economic, or social harm) than was previously known or recognized.

8.4.2 UNANTICIPATED PROBLEMS REPORTING

The investigator will report unanticipated problems (UPs) to the reviewing Institutional Review Board (IRB). The UP report will include the following information:

- Protocol identifying information: protocol title and number, PI's name, and the IRB project number
- A detailed description of the event, incident, experience, or outcome
- An explanation of the basis for determining that the event, incident, experience, or outcome represents an UP

- A description of any changes to the protocol or other corrective actions that have been taken or are proposed in response to the UP

To satisfy the requirement for prompt reporting, UPs will be reported using the following timeline:

- UPs that are serious adverse events (SAEs) will be reported to the IRB and to the study sponsor/funding agency within 10 days of the investigator becoming aware of the event
- Any other UP will be reported to the IRB and to the study sponsor/funding agency within 15 days of the investigator becoming aware of the problem

9 STATISTICAL CONSIDERATIONS

9.1 STATISTICAL HYPOTHESES

1. Test the effectiveness of the combined interventions (data-assisted approach for high intensity medical weight loss) for weight loss in a group of adults with recently diagnosed type 2 diabetes compared to standard of care diabetes self-management education.
H1- The data-assisted approach for HIWL (with or without CGM) will lead to 12% greater weight loss compared to the standard of care DSME.
2. Assess the impact of the data-assisted approach for high intensity medical weight loss on glycemic control outcomes including hemoglobin A1c and diabetes remission rates compared to diabetes self-management education.
H2a- The data-assisted approach for HIWL (with or without CGM) will lead to greater reduction in HbA1c compared to DSME.
H2b- The data-assisted approach for HIWL (with or without CGM) will lead to a greater proportion of participants achieving diabetes remission ($\text{HbA1c} < 6.5\%$) compared to DSME.
3. Explore impacts of adding CGM to the HIWL intervention on time to achieve A1c goals and participant satisfaction.
H3a- The HIWL + CGM approach will achieve A1c goals in a shorter timeframe than HIWL alone.
H3b- Participant satisfaction will be equivalent between the HIWL and HIWL + CGM approaches.
4. Explore differences in healthcare utilization between the treatment groups.
H4- The HIWL groups will have lower healthcare utilization compared to standard of care DSME.

9.2 SAMPLE SIZE DETERMINATION

Power Considerations: Power was estimated assuming a longitudinal framework based on linear mixed models allowing for attrition. The estimated change in weight for the active intervention is 15% at 12 months. The estimated change in weight for the DSME intervention is 3% at 12 months. We anticipate 10% of the study population will be lost to follow up; however, we estimated power based on lost to follow up rates of up to 20%. Using a pooled standard deviation of 6.8% for percent weight loss, we will have > 95% power to detect our hypothesized difference at 12 months with 30 participants per arm.

9.3 POPULATIONS FOR ANALYSES

All participants who are randomized and receive the intervention will be included in the analysis population (intent to treat).

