5.3 LIFESTYLE CONSIDERATIONS

During the study, participants will be asked to:

- Refrain from receiving outside treatment for obesity, including other treatment plans, medications, or pursuing surgery
- Avoid pregnancy

Anyone who engages in either will have their study participation closed out.

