7.1 DISCONTINUATION OF STUDY INTERVENTION/EXPERIMENTAL MANIPULATION

When a subject discontinues from HIWL, HIWL + CGM, or Control groups, but not from the study, remaining study procedures will be completed as indicated by the study protocol. If a clinically significant finding is identified (including, but not limited to changes from baseline) after enrollment, the investigator or qualified designee will determine if any change in participant management is needed. Any new clinically relevant finding will be reported as an adverse event (AE).

The data to be collected at the time of study intervention discontinuation will include the following:

- The reason(s) for discontinuing the participant from the intervention, and methods for determining the need to discontinue
- If the participant is due to complete assessments within 2 weeks of being discontinued from the study intervention, those assessments will be administered at the time of discontinuation; if the next scheduled assessments are more than 2 weeks from the discontinuation date, the discontinued participant will wait for the next scheduled assessment. Thereafter, the participant will be included in all future scheduled assessments, even though not participating in the intervention.

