7.2 PARTICIPANT DISCONTINUATION/WITHDRAWAL FROM THE STUDY

Participants are free to withdraw from participation in the study at any time upon request.

An investigator may discontinue a participant from the study for the following reasons:

- Initiation of a disqualifying weight loss treatment (e.g., bariatric surgery)
- Lost-to-follow up; unable to contact subject (see **Section 7.3, Lost to Follow-Up**)
- Any event or medical condition or situation occurs such that continued collection of follow-up study data would not be in the best interest of the participant or might require an additional treatment that would confound the interpretation of the study
- The participant meets an exclusion criterion (either newly developed or not previously recognized) that precludes further study participation (e.g., becomes pregnant)

The reason for participant discontinuation or withdrawal from the study will be recorded on the Study Discontinuation Case Report Form (CRF). Subjects who sign the informed consent form and are randomized but do not receive the study intervention may be replaced. Subjects who sign the informed consent form, and are randomized and receive the study intervention, and subsequently withdraw, or are discontinued from the study, will not be replaced.

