9.4 STATISTICAL ANALYSES

9.4.1 GENERAL APPROACH

Analyses: In general, two types of analyses will be performed: 1) those aimed at estimation of the difference between intervention groups for outcomes like percent change in body weight and HbA1c, and 2) those aimed at estimating differences in the proportion of participants achieving remission by treatment arm. We will analyze the data based on intention to treat principles. Analysis of covariance will be used to estimate the effect of the intervention on 12-month continuous measures including body weight percent change and HbA1c. The model to be used will include the following covariates: the baseline value of the outcome, gender, and age (to control for possible imbalance due to the small number of participants randomized). 95% confidence intervals will be generated for the intervention effect on these and other outcomes. The proportion of remission between two groups will be compared using a two-sided chi-square test and summarized using an odds ratio (OR) and confidence intervals (CI). The primary outcome will be percent change in initial body weight. Secondary outcomes include change in HbA1c and diabetes status (remission will be indicated by a dichotomous yes or no).

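### The set labelled intent to treat omits randomised participants who do not receive the intervention, an exclusion after allocation that can differ by arm and can bias the 12-month contrast

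*Combined protocol and SAP*

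**What the plan says.** Section 9.3 defines the analysis set in one sentence: "All participants who are randomized and receive the intervention will be included in the analysis population (intent to treat". Section 9.4.1 gives the governing principle: "We will analyze the data based on intention to treat principles". Section 7.2 adds, for those who never start: "Subjects who sign the informed consent form and are randomized but do not receive the study intervention may be replaced". People who start and leave later are not replaced. No section defines what counts as receiving either intervention.

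The Schedule of Activities (1.3) places randomisation, treatment orientation and the first HIWL counselling at week 0. For DSME, Section 6.1.1 asks for an initial class or appointment at some point in month one. The heading of Section 6.3 mentions blinding, but its text covers allocation only.

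On outside treatment, Section 5.3 lists this request: "Refrain from receiving outside treatment for obesity, including other treatment plans, medications, or pursuing surgery". It then says: "Anyone who engages in either will have their study participation closed out". Section 7.2 treats the same event differently. Its list opens "An investigator may discontinue a participant from the study for the following reasons", and the first reason is "Initiation of a disqualifying weight loss treatment (e.g., bariatric surgery". Section 7.1 covers people who stop the intervention but remain in the study: "Thereafter, the participant will be included in all future scheduled assessments, even though not participating in the intervention".

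The 12-month analysis in Section 9.4.1 is an analysis of covariance. No method for missing outcomes is given.

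**The concern.** Intention to treat means everyone randomised, analysed in the assigned arm. Section 9.3 uses the label for a smaller set whose membership is settled after allocation. The replacement rule supports that reading, because it treats non-receivers as places to be refilled.

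The exclusion need not fall evenly. One arm is offered free meal replacements, a connected scale and a digital platform with a target of 15–20% loss. The other is offered education and counselling with a target of 5%. Participants cannot fail to know which they have. The DSME window for a first contact is also longer, so there is more time to become a non-receiver there. With receipt undefined, someone must decide case by case, knowing the arm, who belongs in the primary analysis.

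Close-out for outside obesity treatment is a separate route to the same loss. Such a person has received the intervention and stays in the Section 9.3 set, but may have no 12-month weight. An analysis of covariance with no missing-data rule would in practice drop them.

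The size of the estimate is at stake. Hypothesis H1 names a 12% advantage, and remission counts feed the cost-effectiveness ratio.

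**Working it through.** **1. Inputs from the plan (Sections 4.1 and 9.2).** 90 randomised to three arms of 30; expected loss 15% (active) and 3% (DSME), so a difference of 12 points; SD 6.8 points; loss to follow-up expected at 10%, with power considered up to 20%. Alpha is not stated for the primary test; I assume 0.05 two-sided.

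**2. The plan's own figure.** SE = 6.8 × √(2/n).
- n = 30: SE = 1.756; 12/1.756 − 1.96 = 4.87; power above 99.99%.
- n = 24 (20% lost): SE = 1.963; 12/1.963 − 1.96 = 4.15; power above 99.99%.

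The stated power of more than 95% is reproduced as a lower bound.

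**3. Shift from excluding part of an arm.** Shift in arm mean = fraction removed × difference in 12-month change between those removed and those kept. One person is 1/30 = 3.3% of an arm. The rates are assumptions; the documents give none.
- 3 of 30 removed, 5 points apart: 0.10 × 5 = 0.5 points.
- 6 of 30 removed, 10 points apart: 0.20 × 10 = 2.0 points.
- The same 3–6 people from one HIWL arm, with both HIWL arms pooled (60): 0.05 × 5 = 0.25 to 0.10 × 10 = 1.0 points.

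**4. A wider gap, anchored on the plan's means.** Suppose a fraction f of the active side never starts and loses 0–3%, while those who start lose 15%. The difference in everyone randomised is (1 − f) × 15 + f × (0 to 3) − 3.
- f = 10%: 10.5 to 10.8 points.
- f = 20%: 9.0 to 9.6 points.

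The Section 9.3 set would still estimate about 12, an overstatement of 1.2–1.5 or 2.4–3.0 points.

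**5. Close-out in DSME.** Suppose a fraction f of DSME starts outside treatment that would give 10–15% loss and has no 12-month weight. Omitting them overstates the difference by f × (10 − 3) to f × (15 − 3):
- f = 10%: 0.7–1.2 points.
- f = 20%: 1.4–2.4 points.

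**6. Direction.** Dropping HIWL non-starters who would have lost little raises the contrast. Dropping DSME non-starters who would have lost little lowers it. Losing DSME participants who do well on outside treatment raises it. No sign follows from the documents.

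**7. Can the trial afford the full randomised set?** The check used t-test power and raised the active-arm variance to 6.8² + f(1 − f)(15 − m)², where m is the mean loss in non-starters, averaged with 6.8² for DSME.

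| Scenario | Difference (points) | Power, 30 / 24 per arm |
|---|---|---|
| f = 10%, m = 0 | 10.5 | 99.96% / 99.7% |
| f = 20%, m = 0 | 9.0 | 99.0% / 96.8% |
| Both mechanisms at 20%, extreme values | 6.6 | 82% / 73% |

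In the last row, 20% of the active side loses nothing and 20% of DSME loses 15%: 0.8 × 15 − (0.8 × 3 + 0.2 × 15) = 6.6. Outside that extreme, power gives no reason to exclude or replace anyone.

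**The case against.** The best defence is that the exclusion may be rare and its effect modest. Orientation and HIWL counselling fall at week 0, so if orientation counts as receipt, few in HIWL could be non-starters. DSME is not an empty control either: it includes a weight-reducing diet and counselling. Every shift above rests on assumed rates, and a 12-point planned effect would probably stay significant under most of them. All of this stands and limits the severity. It does not reconcile Section 9.3 with Section 9.4.1, and whether orientation counts as receipt is exactly what the plan leaves open.

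Replacement also does no harm in itself. It is permitted, not required, and randomising more than 90 people is no problem if all of them are analysed.

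A reader might infer more than the text supports:

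- **That Section 5.3 contradicts Section 7.1.** It does not. Section 7.1 concerns people who leave the intervention but not the study; close-out concerns leaving the study. The textual conflict is between Section 5.3, where close-out is mandatory, and Section 7.2, where it is at the investigator's discretion.
- **That close-out is a second exclusion from the analysis set.** Those participants meet the Section 9.3 definition. Theirs is a missing-outcome problem, and it is not certain that no 12-month weight would be taken.
- **That non-starters are selected on how their weight loss is going.** They have no on-treatment weight loss yet. Selection on knowledge of the arm is possible; selection on response is not.
- **That disappointed DSME volunteers bias the result in a known direction.** Step 6 shows that the sign is open.
- **That the trial is declared open-label.** The documents do not use that word for it. Knowledge of the arm is inferred from the interventions and from the absence of any described participant blinding.

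**Conclusion.** The point holds in this form. The plan names intention to treat but defines a population conditional on receipt, leaves receipt undefined, and permits non-receivers to be replaced. No other section restores the full randomised set. Because the exclusion follows allocation and can differ by arm, it can bias the 12-month contrast; the documents do not show that it will.

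On assumed exclusion of 10–20% and a gap of 5–10 points, one arm's mean moves by 0.5–2.0 points, or 0.25–1.0 if the removals come from one of two pooled HIWL arms. The overstatement reaches 3.0 points only if 20% of the active side never starts and loses nothing. Against a planned 12 points, this threatens the size of the estimate more than its significance.

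The missing 12-month weight after close-out is a related but separate gap. It arises from the unreconciled Sections 5.3 and 7.2 and the lack of a missing-data method. Overall this should be fixed, but it does not invalidate the design.

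**What to change.** - **Section 9.3:** define the primary set as 'All randomised participants, analysed in the arm assigned.'
- **Section 7.2:** state that any participant who is replaced remains in the analysis. The replacement sentence can then stay.
- **Sections 5.3 and 7.2:** reconcile mandatory with discretionary close-out. Whichever the sponsor adopts, continue to collect the scheduled weight and HbA1c after close-out where consent allows.
- **Section 9.4.1:** pre-specify a primary missing-data method. Without one, a set of all randomised participants shrinks to complete cases. The linear mixed model already assumed for power in Section 9.2 is a natural choice. It relies on outcomes being missing at random and learns little from someone with no weight after baseline, so it does not replace collecting the data.
- **Sensitivity analyses:** keep the received-intervention set, with receipt defined in advance for each arm, and a version that treats values after outside obesity treatment as missing.

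The cost is protocol and SAP wording plus a few visits already on the schedule. The one trade-off is that the primary estimate will include the effect of any outside treatment, as intention to treat implies; the second sensitivity analysis shows how much that matters.

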9.4 STATISTICAL ANALYSES

9.4.1 GENERAL APPROACH

Analyses: In general, two types of analyses will be performed: 1) those aimed at estimation of the difference between intervention groups for outcomes like percent change in body weight and HbA1c, and 2) those aimed at estimating differences in the proportion of participants achieving remission by treatment arm. We will analyze the data based on intention to treat principles. Analysis of covariance will be used to estimate the effect of the intervention on 12-month continuous measures including body weight percent change and HbA1c. The model to be used will include the following covariates: the baseline value of the outcome, gender, and age (to control for possible imbalance due to the small number of participants randomized). 95% confidence intervals will be generated for the intervention effect on these and other outcomes. The proportion of remission between two groups will be compared using a two-sided chi-square test and summarized using an odds ratio (OR) and confidence intervals (CI). The primary outcome will be percent change in initial body weight. Secondary outcomes include change in HbA1c and diabetes status (remission will be indicated by a dichotomous yes or no).

Cost-Effectiveness Analysis: The most commonly used measure of cost-effectiveness is the incremental cost-effectiveness ratio (ICER), defined as the ratio of between incremental costs (difference in total costs between intervention and control arms) and incremental diabetes remission (difference in the number of patients with remission in the intervention and control arms)³³. This measure is meaningful in contexts where an intervention increases total costs (since the denominator is expected to be positive, with higher diabetes remission in the intervention arm relative to the control arm). However, in our context where total costs include both intervention and non-intervention healthcare utilization, total costs for the intervention arm may be lower (e.g., if diabetes remission is accompanied by fewer emergency department visits or fewer medications). In this situation, we will report two measures: a) the average additional intervention cost for each additional diabetes remission achieved; and b) the average reduction in healthcare utilization cost for each additional diabetes remission achieved. For the secondary outcome of A1c reduction, we will similarly estimate the average cost of achieving one percentage point reduction in A1c and one additional QALY for each arm (Laiteerapong et al. . We will obtain 95% confidence interval of each estimate based on bootstrap resampling (Briggs et al. 1999). We will perform a variety of sensitivity analyses, including alternative healthcare reimbursement rates (e.g., 10 percent higher than Medicare rates).

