3 OBJECTIVES AND ENDPOINTS

OBJECTIVES	ENDPOINTS	JUSTIFICATION FOR ENDPOINTS	PUTATIVE MECHANISMS OF ACTION
Primary			
Test the effectiveness of the combined interventions (data-assisted approach for high intensity medical weight loss) for weight loss in a group of adults with recently diagnosed type 2 diabetes compared to standard of care diabetes self-management education.	Change in body weight (kg) from baseline to 12 months	Body weight is primary target for medical weight loss interventions	
Secondary			
Demonstrate the feasibility of pairing a high intensity medical weight loss treatment for diabetes remission with a digital platform that integrates remote monitoring, patient self-report, and care pathways into a data-assisted and personalized treatment program.	Hemoglobin A1c (%) change from baseline at 3, 6, 9, 12 months; Diabetes remission at 12 months, including partial remission (HbA1c of 5.7-6.4% without the use of anti-diabetes medications) and complete remission (HbA1c of 5.7-6.4% without the use of anti-diabetes medications);	As a result of weight change, we expect to see changes in glycemic control.	Reductions in fat mass due to energy restriction, leading to less insulin requirements and greater use of fat stores to make up the energy deficit.
Tertiary/Exploratory			
Demonstrate the impact of including CGM as part of the remote monitoring system with the data-assisted approach for high intensity medical weight loss treatment.	Patient satisfaction with CGM; length of time to achieve A1c goals; study retention	CGM provides immediate feedback to patients about glycemic control. We expect this to improve behavioral reactions and future choices in a shorter term.	Feedback loops with relevant data and clear actions leading to more decisive improvements in biomarkers.
Compare estimated healthcare expenditures and	EuroQOL-5; healthcare utilization from self-report	Intensive weight loss intervention involves cost and time. However,	Weight reduction could decrease healthcare utilization by resolving

OBJECTIVES	ENDPOINTS	JUSTIFICATION FOR ENDPOINTS	PUTATIVE MECHANISMS OF ACTION
utilization between the active treatment groups and the control intervention	and review of medical records	we might expect cost savings due to reduction in weight and improved glycemic control.	obesity related complications and decreasing need for medications and other healthcare.

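### The sample size is planned on a longitudinal mixed model, but the stated analysis is a 12-month ANCOVA with no missing-data method; power is safe, the effect estimate less so

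*Combined protocol and SAP*

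**What the plan says.** Section 9.2 describes the planning model: "Power was estimated assuming a longitudinal framework based on linear mixed models allowing for attrition". It expects 10% loss to follow-up and considers up to 20%. It gives neither the number of visits nor the within-person correlation.

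Section 9.4.1 describes the analysis: "Analysis of covariance will be used to estimate the effect of the intervention on 12-month continuous measures including body weight percent change and HbA1c". On the terms in that model it says: "The model to be used will include the following covariates: the baseline value of the outcome, gender, and age". There is no visit term, and no mixed or repeated-measures model appears anywhere in 9.4. No imputation or other missing-data method is given for any efficacy outcome. The only sensitivity analyses mentioned belong to the cost-effectiveness work.

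The data for a longitudinal analysis will exist. The schedule in section 1.3 marks body weight and HbA1c at weeks 12, 24, 36 and 52. Section 3 lists as a secondary endpoint "Hemoglobin A1c (%) change from baseline at 3, 6, 9, 12 months", while 9.4.1 names a model for the 12-month value only.

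Sections 9.3 and 9.4.1 call the analysis intention to treat. Section 7.1 keeps assessing people who stop the intervention but stay in the study. Sections 7.2 and 7.3 provide for withdrawal and loss to follow-up, after which no 12-month weight can be expected.

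**The concern.** The planning model and the analysis model treat dropout differently. A mixed model keeps a participant who has a week-24 weight but no week-52 weight, and uses the early weight to inform the 12-month comparison. A 12-month ANCOVA with nothing added leaves that participant out. The intention-to-treat label does not supply the missing value, so the plan leaves the handling of dropouts to be settled later, possibly after the data have been seen.

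At stake is the treatment estimate. If people who respond poorly leave more often, and one arm loses more people than the other, those with a 12-month weight are a differently selected group in each arm. Baseline, sex and age cannot correct for this, because the selection acts through weights measured after baseline.

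Two features of the protocol make such loss plausible, though they do not establish it. Section 5.3 closes out anyone who takes up outside obesity treatment, which poor responders may be more likely to seek. Contact also differs by arm: the weight-loss arms have weekly clinician visits for four weeks and then platform-guided follow-up, while the DSME arm has an initial session and then at least quarterly appointments.

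**Working it through.** **1. The plan's own power figure.** Inputs from section 9.2: "The estimated change in weight for the active intervention is 15% at 12 months"; the matching figure for DSME is 3%, and the pooled SD is 6.8 points. The difference is 15 − 3 = 12 points. Alpha is not stated for this test; two-sided 0.05 is assumed, in line with the planned 95% intervals. The mixed-model calculation cannot be rebuilt without a correlation and a number of visits, so the check uses the stated single-time-point analysis. It counts only participants with 12-month data and credits the covariates with no reduction in SD.

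Formula: SE = 6.8 × √(2/n); power ≈ Φ(12/SE − 1.96). The last column uses a noncentral t with 2n − 2 − 3 degrees of freedom.

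| n per arm | Loss | SE | 12/SE | Power (z) | Power (t) |
|---|---|---|---|---|---|
| 30 | 0% | 1.756 | 6.83 | 99.9999% | 99.9999% |
| 27 | 10% | 1.851 | 6.48 | 99.9997% | 99.9994% |
| 24 | 20% | 1.963 | 6.11 | 99.998% | 99.997% |

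The stated figure, "we will have > 95% power to detect our hypothesized difference at 12 months with 30 participants per arm", is a lower bound and is met in every row. With 24 per arm, two-sided alpha of 0.0167 still gives 99.98%. An SD of 10 gives 98.2%, and power falls below 95% (to 92.3%) only when the SD is raised to 12. Changing the model changes power by less than 0.01 percentage point.

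**2. How many participants are omitted by default.** 90 × 0.10 = 9; 90 × 0.20 = 18.

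**3. Size of the bias.** This was simulated. Taken from the documents: 60 against 30 (H1 pools the two weight-loss arms against DSME), true difference 12, SD 6.8. Assumed, because the documents give no figure: correlation between visits 0.8 to 0.9, and dropout odds multiplied by 2.7 to 4.5 for each SD of poorer response at the previous visit. Dropout is missing at random by construction.

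| Loss, weight-loss arms / DSME | Overall loss | 12-month data only | Likelihood, all visits |
|---|---|---|---|
| 20% / 10% | (12 + 3)/90 = 16.7% | 12.4 to 12.6 | 11.9 to 12.1 |
| 10% / 20% | (6 + 6)/90 = 13.3% | 11.3 to 11.6 | 11.9 to 12.1 |
| 20% / 20% | 20% | no bias in the difference | no bias in the difference |

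The error is about 0.4 to 0.7 points, or 0.4/12 = 3% to 0.7/12 = 6% of the effect. Its sign follows the arm with the greater loss. At about 10% overall loss split 2:1 between arms it is about 0.2 to 0.4 points. With dropout odds of only 1.5 per SD it stays under 0.3 throughout.

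**4. Against the sampling error.** With 48 and 27 observed, SE = 6.8 × √(1/48 + 1/27) = 1.64. With 54 and 24 it is 1.67. The bias is therefore about a quarter (0.4/1.67) to two-fifths (0.7/1.64) of a standard error. Nominal 95% intervals covered the true value 93% to 96% of the time.

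**5. A case that is not missing at random, for scale.** If 20% are lost in both arms and all of them are back at baseline weight, the difference is 0.8 × 15 − 0.8 × 3 = 9.6 points, with power of 99.9%. That shift of 2.4 points is larger than anything in step 3.

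**The case against.** The case on the other side has several parts.

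- **Completer analysis.** A reader might infer that the plan prescribes one. It does not: no section says so, 9.3 and 9.4.1 invoke intention to treat, and 7.1 keeps following people who stop the intervention. Lacking a 12-month weight is not the same as stopping the intervention. What stands is that the handling of missing 12-month weights is undefined, and omission is what the named model does if nothing is added.
- **Sample size.** A reader might infer that the mismatch undermines it. Step 1 shows that it does not.
- **Interim HbA1c.** It would go too far to call these values unused. They serve the exploratory endpoint on time to A1c goals and the quarterly medication review. What is missing is a named model for the 3, 6 and 9-month changes. The interim weights have no stated analysis.
- **The bias is small and rests on assumptions.** This stands. The dropout odds, the correlations and the imbalance between arms are not in the documents, both unequal scenarios exceed the expected 10% loss, and a true 12-point effect would be detected either way.
- **The mixed model's advantage is built in.** This also stands: the simulated dropout is missing at random, the condition under which likelihood methods work. Close-out for outside treatment may not meet it.
- **Precision.** A reader might expect the mixed model to give a tighter estimate. At these dropout odds the ratio of complete-case to likelihood variance ran from 0.90 to 1.04, so no dependable gain can be claimed.

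**Conclusion.** The concern holds in a limited form. Sections 9.2 and 9.4.1 name different models, and the one to be used has no missing-data method, sets aside the interim weights and leaves three listed HbA1c time points without a named analysis.

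The consequence is possible bias in the estimate, with no loss of power. The bias is about 0.4 to 0.7 points on 12 under the assumed response-related loss of 20%/10% or 10%/20%, about 0.2 to 0.4 at about 10% overall loss split 2:1, and nil if loss is equal. It would not reverse a 12-point effect, but it would weigh proportionally more on a smaller one. The mixed model removes it only if dropout is missing at random. The change is worth making because the better method uses data already scheduled and the model that the sponsor already planned on.

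**What to change.** Make the primary analysis a linear mixed model for repeated measures over weeks 12, 24, 36 and 52. Include arm by visit, baseline value by visit, sex and age, with an unstructured covariance (four visits, so 4 × 5/2 = 10 parameters), and name the week-52 contrast as primary. Use the same model for HbA1c at 3, 6, 9 and 12 months.

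Keep the 12-month ANCOVA as a sensitivity analysis. Add one missing-not-at-random check, for example with dropouts regaining towards baseline; step 5 of the working suggests that this assumption can matter more than the choice between the two models.

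ANCOVA with multiple imputation from the interim visits would be an acceptable alternative. Whichever is chosen, align section 9.2 with it, and state the visits and correlation assumed if the mixed model stays as the basis for power.

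The cost is plan wording and a little more analysis work. The downside is reliance on a missing-at-random assumption, which the sensitivity check is there to probe.
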